#### **15.3.** Adverse Events Reporting

#### 15.3.1. Reporting Requirements

- The adverse events reporting period for this trial begins upon receiving the first dose of investigational product and ends on the last day of the Safety Evaluation Period.
- All adverse events that occur in trial subjects during the adverse events reporting period specified in the protocol must be reported to the Sponsor, whether or not the event is considered study medication related.
- In addition, any known untoward event that occurs subsequent to the adverse events reporting period that the investigator assesses as possibly related to the study medication should also be reported as an AE.
- The investigator also should comply with the IRB/IEC procedures for reporting any other safety information.
- All AEs should be reported to the Sponsor within 10 calendar days.
- All SAEs must be reported to Sponsor immediately (within 24 hours) upon knowledge.
- The Sponsor shall forward these AE reports to the Data Safety Monitoring Board.
- The Sponsor shall forward all SAE reports to the Data Safety Monitoring Board immediately upon receipt.

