## **Brief Description of the Protocol:**

This is a single center, open label study comparing CryoVaxTM personalized anti-tumor vaccine protocol combining the cryoablation of a selected metastatic lesion with intra-lesional immunotherapy with AlloStim® alone. The treatment schedules both have the following steps: (1) priming with intradermal AlloStim®; (2) vaccination combining cryoablation with intratumoral AlloStim® or intravenous AlloStim® dosing in the place of cryoablation; (3) activation with intravenous AlloStim®; and (4) booster with intravenous AlloStim®. All subjects are followed for safety during the dosing period and until 28 days following the last dose (Safety Evaluation Period"). All subjects are continued to be followed for survival after the Safety Evaluation Period.

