## **Clinical Laboratory Tests:**

Changes in laboratory levels are evaluated in order to determine if the study drug is related to, or might cause, any changes in serum chemistry, hematological function, liver or kidney function, or maintenance of immune self-tolerance (autoimmune tests). All subjects will be monitored for changes in laboratory values in CBC, CMP (including liver function test, kidney function tests) lipase, total IgG and IgM, erythrocyte sedimentation rate, and CRP at baseline and weekly during the Safety Evaluation Period. Coagulation studies (PT, PTT, and INR) are conducted at baseline and prior to interventional procedures (biopsy, cryoablation and intratumoral injections). An autoimmune panel will be assessed on day 0 (baseline, prior to drug administration) and on the last day of the Safety Evaluation Period.

The laboratory reports should be de-identified and provided to the Sponsor. The Sponsor will provide graphs indicating the changing values of select markers. The graphs will be provided to the PI or designee for review and indication of clinical significant findings.

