# **11. STUDY PLAN AND PROCEDURES**

# 11.1. OVERALL STUDY PLAN

Subjects will be screened for eligibility for the study. The screening process involves examining medical records to determine eligibility based on the IC/EC criteria. After obtaining informed consent, subjects will undergo physical exam, provide blood for lab analysis (CBC, CMP, total IgG and IgM, lipase, erythrocyte sedimentation rate, and CRP), an ultrasound of the liver, and a CT scan. The results of these baseline tests will be reviewed by the Principal Investigator (PI) and the Sponsor's medical monitoring team to determine if the subject still meets IC/EC. In schedule A-1, the study interventional radiologist will determine if the subject has a lesion assessable for cryoablation. If the subject meets IC/EC criteria, a biopsy and tumor harvest procedure will be conducted.

When the PI and the Sponsor agree that all IC/EC criteria are met, the subject is accrued/ enrolled in the study and assigned a protocol number. The enrollment date will be documented in CRF/eCRF. Upon accrual, the study site develops an appointment schedule for the subject and sends to the Sponsor for approval. Upon approval, the subject is notified of the schedule. The Sponsor will produce and ship AlloStim® in accordance with the approved schedule.

AlloStim® will be formulated in Israel by the Sponsor, packaged in validated temperaturecontrolled container and delivered by specialized courier service to the study site at least one day before the established treatment schedule day. AlloStim® is stable in formulation for at least 72 hours. All protocol required CT scans will be conducted at a radiology center. Cryoablation, intratumoral AlloStim® and voluntary tumor biopsies will be conducted at a radiology center.

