#### 11.2.4. Tumor Assessment

CT scan of the Head/Chest/Abdomen/Pelvis with and without contrast (if tolerated) will be conducted at baseline and Day 91. All subjects accrued in schedule A-1 will also be evaluated at baseline to confirm they have a liver lesion that can be readily visualized and safely approached percutaneously for cryoablation.

Subjects will undergo mandatory tumor biopsies of at least one selected target lesion (not lesion targeted for ablation) at baseline, during intratumoral injections (day 21 Schedule A1 and on Day 91.

The intratumoral procedures use a trocar that will have already been inserted into the tumor to conduct the intratumoral injection and thus these biopsies will not add an additional invasional procedure.

In order to obtain information on the longitudinal changes in the immune cell patterns of tumors as well changes in tumor size, biopsies will be collected for subjects who consented under a separate inform consent. These additional biopsies will be conducted only if subjects separately consent. Failure to consent for the intermediary biopsy procedures will not disqualify subjects.

The biopsies material should be placed in containers supplied by the Sponsor. The samples should be labeled with protocol number, subject study ID, date of birth, date of sample collection and sample time point (protocol day). The containers should be kept at room temperature (RT) and delivered to Sponsor's histology lab within 24h of collection to:

> [name], MD (Pathologist): Immunovative Clinical Research, Inc., [name]

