| Chemistry Profile (CMP)                | Х        |       | х     | х     | Х            | х     | х             | х             | х         |
| Inflammation Biomarkers*               | X        |       | х     | х     | Х            | x     | х             | х             | х         |
| Pregnancy Test (β-HCG)                 | Х        |       |       |       |              |       |               |               |           |
| Coagulation profile (PT, PTT, INR)     | Х        |       |       | х     |              |       |               |               |           |
| Autoimmune Panel**                     |          | х     |       |       |              |       |               |               | Х         |
| HLA engraftment test                   | X        |       |       |       |              |       |               |               | Х         |
| Research blood draw***                 |          | х     |       |       | Х            |       | х             | х             |           |
| Concomitant Medications                | X        | х     | х     | X     | Х            | х     | х             | х             |           |
| Adverse Events                         |          | х     | х     | х     | Х            | х     | х             | х             | Х         |

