#### **15. ADVERSE EVENTS**

An adverse event (AE) is any untoward medical occurrence in a trial subject that has been administered the study drug; the event does not necessarily have to have a causal relationship with AlloStim® treatment or usage.

All observed or volunteered AEs, regardless of causal relationship to the investigational product, will be recorded as an adverse event on a supplied case report form (CRF) or electronic CRF (eCRF). Events involving adverse drug reactions, illnesses with onset during the study, or exacerbations of preexisting illnesses should also be recorded as AEs.

Exacerbation of pre-existing illness, including the disease under study, is defined as manifestation (sign or symptom) of the illness that indicates a significant increase in the severity of the illness as compared to the severity noted at the start of the trial and the known normal course of disease progression for stage IV colorectal cancer. This may include worsening or increase in severity of signs or symptoms of the illness, increase in frequency of signs and symptoms of an intermittent illness, or the appearance of new manifestations/complications. Exacerbation of a pre-existing illness should be considered when a subject requires new or additional concomitant drug or non-drug therapy for the treatment of that illness during the trial.

Lack of, or insufficient clinical response, benefit, efficacy or therapeutic effect, should not be recorded as an AE. The investigator must make the distinction between exacerbation of preexisting illness and lack of therapeutic efficacy. The investigator can take into consideration the results of radiology and pathology exams and immunological monitoring data when making this assessment.

In addition, abnormal objective diagnostic procedures findings (e.g., abnormal laboratory test results) should be recorded as an AE if it is fulfills one or more of the following:

- Results in subject's withdrawal by the Investigator;
- Is associated with an SAE;
- Is associated with clinical signs or symptoms;
- Is considered by the physician to be of clinical significance;
- Requires the subject to have study therapy discontinued, modified, or interrupted;
- Requires the subject to receive specific corrective therapy; and
- Requires diagnostic evaluation to assess the risk to the subject.

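### Non-serious complications of the baseline biopsy, and of a Day 91 biopsy when the final booster is not given, drop out of the adverse-event data, and Table 1 contradicts the text on coagulation testing before biopsy

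*Combined protocol and SAP*

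**What the plan says.** **Biopsies.** Section 11.2.4 says "Subjects will undergo mandatory tumor biopsies of at least one selected target lesion", at baseline, at the Day 21 intratumoral procedure in A-1, and on Day 91. Section 12.2 lists the screening biopsy as mandatory. Section 11.1 places the first one before enrollment: "If the subject meets IC/EC criteria, a biopsy and tumor harvest procedure will be conducted".

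**Start of AE collection.** Section 15 defines an AE as "any untoward medical occurrence in a trial subject that has been administered the study drug". Section 15.3.1 adds: "The adverse events reporting period for this trial begins upon receiving the first dose of investigational product". The AE row is blank at baseline in Tables 1 and 2. Section 16.1.4 summarises only events from the first treatment onward.

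**End of AE collection.** The period "ends on the last day of the Safety Evaluation Period" (15.3.1). The abstract (Brief Description of the Protocol) sets that length: "All subjects are followed for safety during the dosing period and until 28 days following the last dose". After it closes, 15.3.1 asks only for events judged possibly related to study medication, and 16.1.3 leaves later AEs out of the safety evaluation. However, both tables mark AEs at Day 91, and Section 15.1.3 requires AE questioning at each clinic visit and at least monthly by telephone in follow-up.

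**Coagulation.** Under Clinical Laboratory Tests, the abstract says that coagulation studies "are conducted at baseline and prior to interventional procedures (biopsy, cryoablation and intratumoral injections". Table 1 (A-1) marks the coagulation profile at baseline and Day 14 only. Table 2 (A-2) marks baseline, Day 14 and Day 77.

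**The concern.** The trial imposes an invasive procedure before the first dose and another near the end of treatment, then defines its primary safety data by dosing alone. A non-serious complication of the first biopsy cannot be an AE, because the subject has not yet had study drug. Whether a complication of the last biopsy counts depends on whether the subject took the final booster, which has nothing to do with the biopsy. In a study of this size, one lost procedural event changes the safety description.

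Section 15.3.3 adds to the problem. It records relatedness to study medication or to tumor, so an event caused by a study procedure has no category of its own.

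The coagulation point is a plain contradiction. A site working from Table 1 and a site working from the abstract would do different things before the A-1 Day 91 biopsy.

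**Working it through.** **Baseline biopsy.** Inputs: screening runs from Day -14 to Day -1 (Tables 1 and 2), and the first dose is on Day 0. Every baseline biopsy therefore precedes the reporting period. Four provisions point the same way: the definition in Section 15, the start date in 15.3.1, the blank baseline AE cells, and the summary rule in 16.1.4. The safety population also requires a dose (abstract, Statistical Analysis), so a subject who never reaches Day 0 because of a biopsy complication appears in no safety table.

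For serious events the position is unclear:
- Section 15.2.2 asks for any serious adverse event (SAE) or death during the study, whatever the cause.
- Section 15.2 treats seriousness as a way of deciding whether an AE qualifies as an SAE, and Section 15 has already limited AEs to dosed subjects.
- Table 8 includes not having received study drug as a ground for a Not Related assessment, which suggests that events in undosed subjects were contemplated.

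**Day 91 biopsy.** Formula: end of period = day of last dose + 28. Dose days come from the abstract, Section 8 and Tables 1 and 2.

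| Last dose | A-1 | A-2 |
|---|---|---|
| No booster | 28 + 28 = Day 56 | 28 + 28 = Day 56 |
| First booster only | 56 + 28 = Day 84 | 49 + 28 = Day 77 |
| Final booster given | 84 + 28 = Day 112 | 77 + 28 = Day 105 |

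Day 91 is inside the period only if the last dose falls on or after Day 91 - 28 = Day 63. On the planned dose days, only the final booster achieves that. Dosing that stops before Day 28 closes the period earlier still.

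Section 12.1 allows CT scans to move by one week either way. If the biopsy moves with the scan, the earliest date is Day 84. For an A-1 subject with one booster that is the last day of the period, so a complication appearing afterwards is still outside. For an A-2 subject with one booster, Day 84 is already past Day 77.

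**A-1 Day 21 biopsy.** This falls on a dosing day, so it is inside the period for a subject treated on schedule.

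**Coagulation.** Days from the last tabled test to the Day 91 biopsy: A-1, 91 - 14 = 77; A-2, 91 - 77 = 14. The text requires a test before biopsy. Table 1 has no mark between Day 14 and Day 91.

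**The case against.** A reader might infer that the mandatory biopsies fall outside safety monitoring altogether. The documents do not support that. The A-1 Day 21 biopsy is inside the period, and so is the Day 91 biopsy when the final booster is given. Both tables mark AEs at Day 91, Section 15.1.3 requires monthly questioning, and Section 15.2.2 requires SAE reports of any cause through the last follow-up visit. So at Day 91 events may well be ascertained. What remains is that 15.3.1 does not require a non-serious, biopsy-related event to be reported after the period, and 16.1.3 excludes it even if it is recorded. The passages conflict.

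The biopsy may also be less compulsory than stated. Section 11.1 and Appendix 1 call biopsies voluntary, and Section 17.1 says that refusing serial biopsies does not exclude a subject. Section 11.2.4 separates mandatory biopsies from additional ones needing separate consent, which may explain part of this, but the wording is not reconciled. Nor does any section say whether the Day 91 biopsy remains due for a subject who stops early.

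A reader might also infer that the Day 91 gap will be common. The table above lists dosing patterns, not subjects, and the documents give no booster uptake. The abstract and Section 8 call the A-1 boosters optional. For A-2 the abstract does, but Section 8 does not.

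On coagulation, the abstract does require the test, and Appendix 1 requires review of coagulation studies for subjects having IV conscious sedation. The tables have other missing marks (Table 1 has no Day 21 biopsy; Table 2 has no Day 91 CT), so this may be clerical. It is still a contradiction in the table that sites use. The prior study's laboratory abnormalities in Section 6.6.1 should not be read as evidence of bleeding risk: they come from mixed cancers, are not bleeding outcomes, and the 7 low-platelet cases among 42 subjects were all Grade 1 or 2.

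Finally, opening AE collection at first dose can be defended where the question is drug toxicity. That supports keeping treatment-emergent tables as they are. It does not support leaving complications of a required pre-dose procedure uncollected.

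**Conclusion.** The point holds in three limited parts.

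1. Non-serious complications of the baseline biopsy are never captured as AEs. This applies to every subject who has that biopsy, dosed or not. Whether serious pre-dose events are captured is unclear.
2. If the final booster is not given, the period ends on Day 56 or 84 (A-1) or Day 56 or 77 (A-2). A non-serious complication of a Day 91 biopsy is then outside the reporting period and excluded from the safety evaluation, despite the AE mark at that visit. This assumes that the Day 91 biopsy is still done in such subjects. How many there will be cannot be derived from the documents.
3. Table 1 contradicts the abstract on coagulation testing before biopsy. The last tabled test is 77 days before the A-1 Day 91 biopsy, against 14 days in A-2.

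The sponsor should correct these because safety is the primary endpoint. They do not show that biopsies go unmonitored in general or that a bleeding hazard has been observed.

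**What to change.** 1. **Start of collection.** In Sections 15 and 15.3.1, begin AE and SAE collection at the first study-specific procedure after consent, including subjects who are never dosed. Add a baseline AE mark to Tables 1 and 2. List pre-dose events separately, so that the treatment-emergent tables in 16.1.4 are unchanged. In 15.3.3, add study procedure as a relatedness option.
2. **End of collection.** In 15.3.1 and 16.1.3 together, extend the reporting and analysis window to the later of 28 days after the last dose and the first scheduled follow-up contact after any Day 91 biopsy. Changing 15.3.1 alone would leave the exclusion in 16.1.3 in force. The monthly telephone contact already planned (abstract, Survival; Section 15.1.3) can serve.
3. **Reconciliation.** Bring the Table 1 coagulation row and the abstract's Clinical Laboratory Tests text into agreement; the timing is for the sponsor and investigators to settle. Also reconcile the mandatory biopsy wording (abstract, Histopathology Assessment; 11.2.4; 12.2) with the voluntary wording (11.1; 17.1; Appendix 1), and state whether the Day 91 biopsy applies to subjects who stop dosing early.

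**Cost.** Amendment wording, a few extra AE form lines and one additional listing. The AE window change needs no new contact. Any effect of item 3 on testing depends on how the passages are reconciled.

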#### **15.3.2. IND Safety Reports**

The sponsor will notify FDA and all participating study investigators of an IND safety report that are Serious and Unexpected Suspected Adverse Reaction (21 CFR 312.32(c)(1)(i)) within 7 or 15 day report, but no later than 15 calendar days as follows:

- For any Unexpected Fatal or Life-threatening event associated with the use of the study drug, the Sponsor notifies the FDA of the SAE by telephone or fax as soon as possible, but no later than **seven (7) calendar days** after initial receipt of the SAE. Then Sponsor will follow with the written report (via MedWatch Form 3500A) no later than **15 days since the occurrence.**
- For any Serious and Unexpected, Non-fatal event associated with the use of the study drug, the Sponsor notifies the FDA as soon as possible, but no later than **15 days** after initial receipt of the event.

All other safety information will be submitted to FDA at the end of Part 1 and in the annual report.

#### 15.3.3. Reporting Adverse Events in the (e)CRFs

The investigator is to report all directly observed adverse events and all adverse events spontaneously reported by the trial subject. In addition, each trial subject will be questioned

about adverse events at each clinic visit following initiation of treatment (toxicity assessment).

Data on all adverse events (serious and non-serious, related or not related) will be collected in the CRFs/eCRF. Minimum requirements of adverse event data to be recorded are type of event, start and stop dates, highest severity grade, seriousness, action taken, outcome, and relatedness to either study medication or tumor.

#### **15.3.4. SAE Contact Information**

All AEs should be reported to the Sponsor every 10 days by email to [contact]. The Sponsor shall forward these AE reports to the Data Safety Monitoring Board.

All SAEs must be reported to Sponsor immediately (within 24 hours) upon knowledge and sent by email to [contact].

# 15.4. ALLOSTIM® INFUSION-RELATED ALLERGIC OR AUTOIMMUNE TOXICITY

In this study, subjects will continue to be closely monitored for infusion reactions, any allergic or autoimmune toxicity Grade 3 and higher and other study drug related Grade 3 and higher toxicities. Physicians should always remain vigilant for signs and symptoms of severe hypersensitivity reactions.

Symptoms occurring during or following infusion of the investigational treatment may also be defined according to adverse event categories, such as allergic reaction, anaphylaxis, autoimmune disorder or cytokine release syndrome (Immune system disorders). The NCI-CTCAE version 4.03 definition of Immune system disorders is provided in Table 9.

In the setting of symptoms occurring during or following infusion of the investigational treatment, investigators are encouraged to use the adverse event term listed below and any additional terms (including those not listed here) that best describe the event. Those events described above should be graded as follows:

| Adverse
Event     | Grade 1   | Grade 2   | Grade 3  | Grade 4  | Grade 5 |
|----------------------|---|---|--|--|---------|
| Allergic
reaction | Transient
flushing or
rash,
drug fever <38
degrees C
(<100.4
degrees F);
intervention
not indicated | Intervention or
infusion
interruption indicated;
responds promptly to
symptomatic
treatment
(e.g., antihistamines,
NSAIDS, narcotics);
prophylactic
medications
indicated for $\leq$ 24 hrs | Prolonged (e.g., not
rapidly responsive to
symptomatic
medication and/or brief
interruption of
infusion); recurrence of
symptoms following
initial improvement;
hospitalization indicated
for clinical sequelae
(e.g., renal impairment,
pulmonary infiltrates) | Life-threatening
consequences;
urgent
intervention
indicated | Death   |
| Autoim               | Asymptomatic;   | Evidence of   | Autoimmune reactions   | Life-  | Death   |

#### Table 9 NCI-CTCAE v 4.03 Infusion-related Allergic or Autoimmune Toxicity

Protocol Date: December 23, 2014 Amendment Date: September 12, 2017 Page 69 of 94

| Adverse
Event                | Grade 1   | Grade 2   | Grade 3   | Grade 4   | Grade 5 |
|---------------------------------|---|---|---|---|---------|
| mune
disorder                | serologic or
other evidence
of autoimmune
reaction, with
normal organ
function;
intervention not
indicated | autoimmune
reaction involving a
nonessential
organ or function
(e.g., hypothyroidism)   | involving major organ
(e.g., colitis, anemia,
myocarditis, kidney)  | threatening
consequences;
urgent
intervention
indicated                       |         |
| Cytokine
release
syndrome | Mild reaction;
infusion
interruption
not
indicated;
intervention
not
indicated                             | Therapy or infusion
interruption indicated
but
responds promptly to
symptomatic
treatment
(e.g., antihistamines,
NSAIDS, narcotics,
I.V.
fluids); prophylactic
medications indicated
for $\leq 24$ hrs | Prolonged (e.g., not
rapidly responsive to
symptomatic
medication
and/or brief
interruption
of infusion); recurrence
of symptoms following
initial improvement;
hospitalization
indicated
for clinical sequelae
(e.g.,
renal impairment,
pulmonary infiltrates) | Life-
threatening
consequences;
pressor or
ventilator
support
indicated | Death   |

The following are treatment guidelines for AlloStim® infusion reactions:

#### Grade 1

- Monitor the subject for worsening of condition.
- For subsequent infusions or IV push, premedicate with 25-50mg diphenhydramine PO/IV, 150mg ranitidine (Zantac) PO or other H-2 blocker, 25-50mg PO indomethacin (or equivalent NSAID). During or after the infusion if showed signs of infusion reactions in prior intravenous dosing (rash, itching, shortness of breath) at the investigator's discretion.

# Grade 2

- Monitor for worsening of condition.
- Administer diphenhydramine hydrochloride 50 mg IV (or equivalent), acetaminophen 650 mg orally for fever, and oxygen.
- For subsequent infusions or IV push, premedicate with 25-50mg diphenhydramine PO/IV, 150mg ranitidine (Zantac) PO or other H-2 blocker, 25-50mg PO indomethacin (or equivalent NSAID). During or after the infusion if showed signs of infusion reactions in prior intravenous dosing (rash, itching, shortness of breath) at the investigator's discretion.
- If steroid therapy is medically indicated, methylprednisone or SoluMedrol should be considered as first choice. Administration of dexamethasone will necessitate dropping the subject from the protocol and censoring data from the first day of administration. Dexamethasone therapy is contraindicated in immunotherapy protocols, as it has been shown to selectively cause apoptosis of activated effector immune cells.
- If a subject should have an infusion reaction to AlloStim®, all attempts should be made to obtain a cytokine blood sample as close to the onset of the event as possible,

at the resolution of the event, and 30 days following the event. The procedure for sample collection and handling is described in a separate procedural manual.

#### Grade 3

- Stop the infusion or IV Push if not completed.
- Administer methylprednisone or SoluMedrol (or equivalent) medications/treatment as medically indicated.
- Subjects who have a Grade 3 infusion reaction will not receive further AlloStim® treatment, but will continue to be followed on the protocol.
- If a subject should have an infusion reaction to AlloStim®, all attempts should be made to obtain a cytokine blood sample as close to the onset of the event as possible, at the resolution of the event, and 30 days following the event. The procedure for sample collection and handling is described in a separate procedural manual.

#### Grade 4

- Stop the infusion or IV push if not completed.
- Administer methylprednisone or SoluMedrol (or equivalent) medications/treatment as medically indicated.
- Hospital admission for observation may be indicated.
- Subjects who have a Grade 4 infusion reaction will not receive further AlloStim® treatment, but will continue to be followed on the protocol.
- If a subject should have an infusion reaction to AlloStim®, all attempts should be made to obtain a cytokine blood sample as close to the onset of the event as possible, at the resolution of the event, and 30 days following the event. The procedure for sample collection and handling is described in a separate procedural manual.

